#### Secondary Analysis

A secondary analysis of the primary endpoint will be based on the ITT analysis set and will employ pattern mixture models using multiple imputation methods. This analysis will use all observed data, including the measurements off treatment. Responses for subjects who discontinued from the study earlier than Week 12 will be imputed based on subjects who discontinued treatment prematurely but subsequently provided off-treatment measurements. The imputation will be done within randomized treatment groups. Data will be analyzed using the same model as in the primary analysis. The treatment comparisons between each of the JNJ-64565111 treatment groups and placebo will be made at Week 12 and adjusted p-values will be provided. Copy control imputation may be used as an alternative to a retrieved dropout approach.

#### Supportive Analyses

Sensitivity analyses for the primary efficacy endpoint will be performed based on the completers' analysis set using the same mixed model for repeated measures as in the primary analysis.

#### Subgroup Analyses

Additional analyses of the primary efficacy endpoint in the mITT analysis set will be performed to assess consistency of treatment effect on percent weight loss for the subgroups defined in Section 2.3 (if there are at least 40 subjects in the subgroup). The interaction of treatment with each of the subgroups will be analyzed based on the MMRM model for the primary efficacy analysis with the addition of the subgroup and the appropriate corresponding 2- and 3-way interaction terms with treatment. If an interaction is observed (2-sided p-value  $< 0.10$ ), then

further evaluations will be performed to assess and explain the nature of the interaction [quantitative or qualitative interaction]. The percentage change from baseline and the 95% CI for differences between each dose of JNJ-64565111 compared to placebo will be presented for the subgroups.

### **Exploratory Analyses**

Additional analysis using a MCP-Mod (Multiple Comparison Procedure – Modelling) approach will be performed to explore the dose response relationship.

## **5.3. Major Secondary Endpoints**

### **5.3.1. Definition**

Secondary efficacy analyses at Week 12 will include the absolute change from baseline in body weight, and the proportion of subjects with  $\geq 5\%$  weight loss.

### **5.3.2. Analysis Methods**

#### **Primary Analysis**

The absolute change in body weight from baseline at Week 12 will be analyzed with an MMRM model similar to the primary efficacy endpoint based on the mITT analysis set.

The proportion of subjects with  $\geq 5\%$  weight loss at Week 12 will be analyzed using the mITT analysis set. Only subjects with observed data at Week 12 while on treatment (up to the last dose of study drug plus 14 days) are eligible to be considered responders ( $\geq 5\%$  weight loss). Subjects without an on treatment weight measurement at Week 12 will be considered non-responders. A logistic regression model including treatment as a fixed effect, and baseline weight as a covariate will be used for the analysis. The odds ratio and adjusted p-value for the treatment comparison between each of the JNJ-64565111 treatment groups versus placebo at Week 12 based on this model will be provided.

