- b) Subjects who prematurely discontinue study drug will require an immediate EOT assessment (either on the day of study drug discontinuation or as soon as possible following study drug discontinuation). Subjects that discontinue study drug early will continue in the study and be assessed with the off-treatment procedures at the subsequent visit(s) per the Schedule of Activities, starting at the next scheduled visit from when study drug was permanently discontinued up to the final Week 12 visit. These off-treatment procedures will include assessment and collection of SAEs, specific AEs of interest (ie, major adverse cardiac events, acute pancreatitis, and possible cases of thyroid neoplasm), vital signs (including body weight), and concomitant medications.
- c) The SAE follow-up visit will be conducted for all subjects approximately 5 weeks after the last dose of study drug to collect serious adverse events since the last visit unless the subject has died, has been lost to follow-up, or has withdrawn consent. Blood samples will also be collected for PK and immunogenicity (ie, anti-drug antibody) measurement. Subjects who prematurely discontinue study drug for any reason prior to Week 12 and have not withdrawn consent, will continue (off-treatment) in the study following the EOT visit and undergo the off-treatment procedures based on the predefined study visit schedule.
- d) Informed Consent must be signed at the screening visit before any study procedures are performed.
- e) Record any medications taken from up to 30 days before screening (and up to 6 months before screening for AHA) until the first dose of treatment phase study drug on Day 1 (baseline) as prestudy therapy in the corresponding eCRF. Concomitant therapy includes all medications taken since the first dose of treatment phase study drug on Day 1.
- f) Subjects will be asked to perform a self-injection of open-label JNJ-64565111-matching placebo (Week -2) or their randomly-assigned study drug (Day 1) at the study site in the presence of the study-site staff. After Day 1, injections may be performed by the subject at home.
- g) A survey will be given to English-speaking subjects to assess subject satisfaction with the experience of self-administering JNJ-64565111 or matching placebo.

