- Initiation and planned continued use of disallowed therapy (see Section [6.5](#), Prestudy and Concomitant Therapy)
- Subject is on glycemic rescue therapy, and after at least 2 weeks on the maximum dose considered appropriate by the investigator, FPG is >180 mg/dL (10.0 mmol/L)

- Subject experiences a SAE of biochemically-confirmed (eg, blood pH, serum β -hydroxybutyrate, anion gap) DKA
- Subject experiences an episode of vomiting assessed as “severe” lasting more than 24 hours and considered to be at least possibly related to study drug without any other potential cause (eg, viral gastroenteritis, food-borne illness).

Subjects who prematurely discontinue study drug prior to Week 12 will require an immediate EOT assessment (either on the day of study drug discontinuation or as soon as possible following study drug discontinuation) and the SAE assessment/follow-up and PK and immunogenicity (ie, ADA) collection at least 5 weeks since the last dose of study drug.

Subjects that discontinue study drug early will continue in the study (off treatment) and will be assessed at the subsequent visit(s) as described in the Schedule of Activities schedule, starting at the next scheduled visit from when study drug was permanently discontinued up to the final Week 12 visit. These off-treatment visits will include assessment and collection of:

- SAEs
- Specific AEs of interest (ie, MACE events, acute pancreatitis, and possible cases of thyroid neoplasm)
- Vital signs (including body weight)
- Concomitant medications

If subjects that discontinued study drug early are unable to return to their site for the scheduled on-site study visit, an alternate contact visit should be conducted with the goal of collecting any SAEs, MACEs (ie, CV death, nonfatal MI and nonfatal stroke), acute pancreatitis, and AEs of thyroid neoplasm. Details regarding discussions via telephone, email, or other methods of contact should be properly documented on subject’s source record and/or eCRF, including date of contact, outcome and responses provided by the subjects. The site may consult subjects’ delegated contact(s) for the off-treatment follow-up if the site is unable to reach the subjects after multiple attempts.

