9.3. Populations for Analyses

For purposes of analysis, the following populations are defined:

Table 5: Subject Population Definitions

Population	Description
Enrolled	All subjects who sign the ICF
ITT analysis set	all subjects who are randomly assigned to a treatment group and have a baseline measurement of body weight
mITT analysis set	all ITT subjects who have at least 1 post-baseline measurement of body weight within 7 days following a dose of study drug and before initiation of any rescue therapy
Completers' analysis set	of all mITT subjects who have completed 12 weeks of double-blind treatment (ie, documented in the eCRF by the investigators that the subject has completed participation in the study through the Week 12 visit) and without initiation of glycemic rescue therapy
Safety analysis set	all randomized subjects who have received at least one dose of study drug

Key: eCRF=electronic case report form; ICF=informed consent form; ITT=intent-to-treat; mITT=modified intent-to-treat.

The primary efficacy analysis, to demonstrate the superiority of JNJ-64565111 compared with placebo on percentage reduction in body weight from baseline to Week 12, as well as all secondary efficacy analyses, will be based on the modified intent-to-treat (mITT) analysis set and will include only those measurements taken up to and including the last dose of study drug plus 7 days and prior to initiation of any glycemic rescue therapy. A secondary analysis of the primary and secondary efficacy endpoints will be based on the intent-to-treat (ITT) analysis set. This analysis will include all measurements. Sensitivity analyses based on the completers' analysis set will also be performed for the primary endpoint.

Efficacy data will be analyzed according to the initial randomization assignment, regardless of the actual treatment received. Safety data will be analyzed according to the predominant treatment received, in the event that a subject receives a treatment other than that to which he/she is randomly assigned.

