## 2. GENERAL ANALYSIS DEFINITIONS

### 2.1. Visit Windows

As subjects do not always adhere to the protocol visit schedule, the following rules are applied to assign actual visits to analysis visits. Listed below are the visit windows and the target days for each visit. The reference day is Study Day 1 (date of first dose). If a subject has 2 or more actual visits in one visit window, the visit closest to the target day will be used as the protocol visit for that visit window. The other additional visit(s) will not be used in the summaries or analyses but they can be used for determination of clinically important endpoints. If 2 actual visits are equidistant from the target day within a visit window, the later visit is used.

All assignments will be made in chronological order. Once a visit date is assigned to a visit window, it will no longer be used for a later time point except for the endpoint. Listed below (Table 2.1.1) are the visit windows and the target days for each visit defined in the protocol. A Post-Week 12 window was created to account for subjects who returned at a timepoint after the Week 12 visit window.

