### **2.2.2. Efficacy Analysis Sets**

- The intent-to-treat (ITT) analysis set will include all subjects who are randomly assigned to a treatment group and have a baseline body weight measurement.
- The modified intent-to-treat (mITT) analysis set includes all ITT subjects who have taken at least one dose of study medication and have at least 1 post-baseline body weight measurement.
- The completers' analysis set will consist of all mITT subjects who have completed 12 weeks of treatment (i.e., documented in the Treatment Disposition eCRF by the investigators that the subject has completed treatment through the Week 12 visit window).

The primary efficacy analysis, to demonstrate the superiority of JNJ-64565111 compared to placebo on percentage reduction in body weight from baseline to Week 12, as well as all secondary efficacy analyses, will be based on the mITT analysis set.

A secondary analysis of the primary and secondary efficacy endpoints will be based on the ITT population (including data after initiation of rescue medication and data after the on-treatment period). This analysis will include all measurements through the Week 12 visit window. Supportive analyses based on the completers' analysis set will also be performed for the primary endpoint.

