#### **Secondary Analysis**

A secondary analysis of the secondary endpoints will be based on the ITT analysis set and will employ pattern mixture models using multiple imputation methods based on information from retrieved dropouts as described above. For the proportion of subjects with  $\geq 5\%$  weight loss, response status will be determined from the imputed continuous response based on subjects who discontinued treatment prematurely but subsequently provided off-treatment measurements. Copy control imputation may be used as an alternative to a retrieved dropout approach.

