#### **5.4.2. Analysis Methods**

The analysis of exploratory endpoints will use the observed data through Week 12 while on treatment (up to the last dose of study drug plus 14 days). The analysis of glycemic parameters (e.g., HbA1c, FPG, fasting insulin, HOMA-B, HOMA-IR) will be based on the measurements prior to rescue medication. The continuous exploratory efficacy endpoints (i.e., change from baseline in BMI, HbA1c, FPG, HOMA-B, HOMA-IR, SBP, DBP, pulse rate, and rate pressure product) with more than one planned post-baseline timepoint will be analyzed using a MMRM model similar to the model used to analyze the primary efficacy endpoint based on the mITT analysis set. An analysis of covariance (ANCOVA) model with treatment as a fixed effect and baseline measurement as a covariate will be used for endpoints with only one planned post-baseline timepoint (e.g., waist circumference, fasting insulin, fasting C-peptide, total cholesterol, LDL-C, and HDL-C). Shift tables will be used to summarize obesity class (Class I = 30 kg/m^2 – 34.9 kg/m^2; Class II = 35 kg/m^2 – 39.9 kg/m^2; Class III = ≥ 40 kg/m^2) at baseline versus end of treatment.

The categorical exploratory efficacy endpoints will be analyzed using a logistic regression model similar to the model used to analyze the proportion of subjects with ≥5% weight loss.

An ANCOVA model with treatment as a fixed effect and baseline measurement as a covariate will be used to analyze the exploratory PRO endpoints. The additional PRO analyses will be described in a separate SAP.

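### Minor: the 5% responder analysis counts a missing on-treatment Week 12 weight as failure, but its mITT set leaves out any dosed subject with no post-baseline weight; the 10% analysis has the same gap

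*SAP*

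**What the plan says.** - **Outcome rule.** SAP 5.3.2 analyses 5% weight loss at Week 12 in the mITT set by logistic regression on treatment and baseline weight. Only a Week 12 weight taken no later than 14 days after the last dose can make a subject a responder. For everyone else: "Subjects without an on treatment weight measurement at Week 12 will be considered non-responders".
- **Analysis set.** SAP 2.2.2 limits mITT to ITT subjects who "have taken at least one dose of study medication and have at least 1 post-baseline body weight measurement". That weight may be on or off drug. The ITT set needs only randomisation and a baseline weight.
- **10% endpoint.** SAP 5.4.2: "The categorical exploratory efficacy endpoints will be analyzed using a logistic regression model similar to the model" used for the 5% endpoint.
- **Protocol.** Sections 9.3 and 9.4.1 also name mITT for this endpoint, with a narrower entry condition: "at least 1 post-baseline measurement of body weight within 7 days following a dose of study drug", and before any rescue therapy. The protocol's model was a longitudinal generalised linear mixed model on observed data. The SAP replaced it with the logistic regression.
- **ITT analysis.** SAP 5.3.2 adds a secondary ITT analysis by multiple imputation, in which "response status will be determined from the imputed continuous response based on subjects who discontinued treatment prematurely" and later gave off-treatment weights. Copy control is the permitted alternative.
- **Error control.** SAP 5.1.1 applies Hochberg across the three doses for each secondary endpoint, so the 5% comparison is a formal one.

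**The concern.** The non-responder rule gives an outcome to every subject who lacks a usable Week 12 weight. The model needs only treatment, baseline weight and that outcome, so it has no use for a post-baseline weight. The mITT condition nevertheless removes some subjects whom the rule would classify as failures. A post-baseline weight made sense for the protocol's longitudinal model, where a subject without one contributes no data. It no longer has that purpose under the SAP's model.

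Two subjects who stop early and have no on-treatment Week 12 weight are then treated differently. One who was weighed once, even off drug, is a failure in the denominator. One who was never weighed again is not counted. Membership of the denominator thus depends on something that happens after randomisation. Each omitted subject raises the response rate of that subject's arm, and the odds ratio moves according to how the omissions fall between arms.

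**Working it through.** **Step 1. Can such a subject exist?** The documents limit the group closely but do not empty it.

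- Routes into mITT: on stopping drug, "Subjects who prematurely discontinue study drug will require an immediate EOT assessment" (Protocol 1.3, footnote b), and weight is scheduled at Week 12/EOT. Off-treatment visits collect weight (Protocol 4.1 and 7.1). Late returns also count: "A Post-Week 12 window was created to account for subjects who returned at a timepoint after the Week 12 visit window" (SAP 2.1).
- Routes out: Day 4 has no weight, so the first scheduled one is at Week 2. Withdrawal of consent and loss to follow-up end participation (Protocol 7.2). For a subject off drug who cannot attend, "an alternate contact visit should be conducted with the goal of collecting any SAEs, MACEs" and other named events; weight is not among the listed goals.

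Let k be the number of dosed subjects in an arm with a baseline weight and no later weight. The documents give no value for k.

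**Step 2. The plan's own figure.** With 47 per arm, SD 4% and difference 2.7% (SAP 1.4), z = 2.7 / (4 × √(2/47)) = 3.27, and power is Φ(3.27 − 1.96) = 90.5% for one comparison at two-sided 0.05. The stated 90% reproduces and is unaffected. The plan gives no figure for the responder endpoint.

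**Step 3. Effect on a response rate.** With x responders among N dosed, x/N becomes x/(N − k), which is larger by the factor N/(N − k). For N = 47 this is 47/46 = 1.022 for k = 1 and 47/44 = 1.068 for k = 3.

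**Step 4. Effect on the odds ratio.** Assumptions: normal percentage change, SD 4%, placebo mean −1% (assumed; not in the documents), drug mean −3.7%.

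- Placebo response: Φ((−5 + 1)/4) = 15.9%, or 7.46 expected responders and 39.54 failures of 47.
- Drug response: Φ((−5 + 3.7)/4) = 37.3%, or 17.51 responders and 29.49 failures.
- Crude odds ratio with k_d drug and k_p placebo failures left out: [17.51/(29.49 − k_d)] / [7.46/(39.54 − k_p)].

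| Left out, drug | Left out, placebo | Odds ratio | Wald 95% CI |
|---|---|---|---|
| 0 | 0 | 3.15 | 1.18 to 8.40 |
| 1 | 1 | 3.18 | 1.19 to 8.50 |
| 1 | 0 | 3.26 | 1.22 to 8.71 |
| 0 | 1 | 3.07 | 1.15 to 8.20 |
| 3 | 3 | 3.24 | 1.20 to 8.74 |
| 3 | 0 | 3.51 | 1.30 to 9.42 |
| 0 | 3 | 2.91 | 1.09 to 7.79 |

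The odds ratio rises when k_d/29.49 exceeds k_p/39.54, that is, when k_p/k_d is below 39.54/29.49 = 1.34. It falls when the ratio is above that.

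**Step 5. Other assumptions.** With a placebo mean of 0%, the odds ratio is 3.34 with none left out and 3.36 with one per arm left out. With −2%, the values are 3.03 and 3.07. For the 10% endpoint at −1% (rates 5.8% and 1.2%), one per arm moves 4.94 to 4.95.

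**Step 6. A constructed close case.** Take 12 of 47 drug and 5 of 47 placebo responders. The unadjusted chi-square p-value is 0.061 with all counted, 0.054 with one drug failure left out, and 0.048 with two. These counts are invented and every omission is placed in the drug arm. The case shows only that a small k could matter in a close result.

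**The case against.** The strongest reply is that nothing is contradictory. The SAP defines mITT openly and applies the failure rule inside it, the protocol names mITT for all secondary endpoints, and using one set for primary and secondary endpoints is a reasonable choice. The affected subjects are in the pre-specified ITT analysis. A subject must also miss the EOT visit, every off-treatment weight and any late return to be left out.

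Much of this stands. It is right that the group is close to empty and that the set was pre-specified. It does not remove the inconsistency. The ITT analysis includes these subjects only by imputation, so no planned analysis applies the stated failure rule to all dosed subjects. The restriction also does no work in the model now specified.

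A reader might infer that the omission favours the drug, because early losses from poor tolerability would fall mainly in the active arms. The documents give no early-loss rates by arm, and the table shows movement in both directions. A reader might also infer inflated type I error; nothing in the documents establishes that.

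A further tempting shortcut is to subtract the mITT count from the safety-set count to obtain k. That is not strictly valid. The safety set does not require a baseline weight (SAP 2.2.3), and safety data are analysed by predominant treatment (SAP 6), whereas efficacy is analysed by randomised arm (SAP 5).

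**Conclusion.** The point holds as a minor one. The 5% and 10% responder analyses treat absence of an on-treatment Week 12 weight as failure, yet leave out randomised, dosed subjects with a baseline weight who have no post-baseline weight at all. If k is zero in every arm, nothing changes. In the illustration, one omission per arm shifts the 5% odds ratio by 0.03, and the most lopsided case shown (three drug, none placebo) shifts it by 0.36, both small against an interval of 1.18 to 8.40. These sizes rest on an assumed placebo mean, normality, equal SDs, 47 dosed per arm, no other missing weights and an unadjusted odds ratio. The primary endpoint and the sample size are not affected.

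**What to change.** In SAP 5.3.2 and 5.4.2, run the 5% and 10% logistic regressions, with the existing non-responder rule, in all randomised subjects who took at least one dose and have a baseline weight, analysed by randomised arm. Report the mITT version alongside. If the sponsor prefers to keep the protocol-named mITT set as the main one, pre-specify the wider analysis as a sensitivity analysis; that is the minimum.

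Report directly, for each randomised arm, the number of dosed subjects with a baseline weight but no post-baseline weight.

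The cost is a short change to the SAP text and a population flag in the programs, with no new data. The downsides are that the responder set would differ from the one used for the primary endpoint, that a departure from the protocol-named set would need to be documented, and that response rates may be slightly lower.

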#### **Secondary Analysis**

A secondary analysis of the secondary endpoints will be based on the ITT analysis set and will employ pattern mixture models using multiple imputation methods based on information from retrieved dropouts as described above. For the proportion of subjects with  $\geq 5\%$  weight loss, response status will be determined from the imputed continuous response based on subjects who discontinued treatment prematurely but subsequently provided off-treatment measurements. Copy control imputation may be used as an alternative to a retrieved dropout approach.

